5.0 Pre-treatment Evaluations

5.1 Dental evaluation

5.2 Nutritional evaluation

5.3 Tobacco and alcohol assessment

5.4 Videofluoroscopic Swallowing (VFSS) Evaluation

5.5 Measurement of whole mouth saliva (sialometry)

5.6 EORTC QLQ C30 and EORTC QLQ H&N

5.7 Physician dysphagia log

5.8 Patient swallowing diary

5.9 Speech Assessment/Head and Neck Health Status Assessment Inventory (HNHSAI)

5.10 ChemoSensory Questionnaire (CSQ)

5.11 Trismus Assessment

Subject Enrollment

Patients will be registered through the Quality Control Committee (QCC) at the Dana-Farber Cancer Institute [contact], [contact]) prior to treatment. Any patient not registered to the protocol prior to the initiation of treatment will be ineligible. The following information will be provided to the QCC:

Name and telephone number of primary oncologist

Protocol name

Patient name, date of birth, and ID number

Primary institution

Date of initiation of radiotherapy

Confirmation of eligibility

Copies of consent form with signatures

6.0 Treatment Program

All patients will undergo their radiation planning and radiation treatment at the Massachusetts General Hospital (MGH). Patients may receive chemotherapy at any of the participating institutions.

6.1 Treatment Planning, Imaging, and Localization Requirements

- 6.1.1** All patients will be immobilized in a custom designed device. Immobilization device should include neck and shoulder immobilization.
- 6.1.2** Treatment planning CT scans (with contrast, unless contraindicated) will be required to define gross target volume and clinical target volume. The treatment planning CT scan should be acquired with the patient in the same position and using the same immobilization device as for treatment. All tissues to be irradiated must be included in the CT scan. CT scan thickness should be 25 mm or smaller slices through the region that contains the primary target volumes. The regions above and below the target volume may be scanned with slice thickness of 0.5 cm. Treatment planning CT must be within 21 days of start of radiation.
- 6.1.3** MRI scans (with gadolinium unless contraindicated) are required in assisting the delineation of the treatment volume on planning CT scans.
- 6.1.4** The GTV, CTV, and normal tissues must be outlined on all CT slices in which the structures exist. GTV and CTV are defined in section 6.2.1.

6.2 Volume and ICRU Reference Point Definitions

The definition of volumes will be in accordance with the 1993 ICRU Report #50: Prescribing, Recording, and Reporting Photon Beam Therapy.

- 6.2.1** The Gross Tumor Volume (GTV) is defined as all known gross disease determined from CT, MRI, clinical information, and/or endoscopic findings. Grossly positive lymph nodes are defined as any lymph nodes greater than 1 cm or nodes with a necrotic center.
- 6.2.2** The Clinical Target Volume (CTV) is defined as the GTV plus areas that are considered to contain potential microscopic disease. Three different CTVs will be defined, namely CTV₆₀ for the tumor in the primary site and the high risk nodal regions and CTV₅₀₋₅₄ for the low risk nodal regions. Please note that there is no set margin between each GTV and its CTV.

6.2.3 The Planning Target Volume (PTV) will provide a margin of 3 mm around each CTV (namely PTV₇₀, PTV₆₀, PTV₅₀₋₅₄) to compensate for the variabilities of treatment set up and internal organ motion.

6.3 Critical Normal Structures

Critical normal structures, including the brainstem, spinal cord, optic nerves, chiasm, retina, eyes, temporal lobes, and frontal lobes should be outlined in all cases. Parotid glands, submandibular glands, oral cavity, cochleas, temporomandibular joints, mandibles, pituitary glands, hypothalamus, and lacrimal glands should also be outlined.

6.4 Treatment Planning

The treatment plan used for each patient will be based on an analysis of the volumetric dose, including dose-volume histogram (DVH) analyses of the PTV and critical normal structures.

6.4.1 Dose Specifications

6.4.1.1 The gross primary tumor and lymph node metastasis of greater than 2 cm, PTV₇₀, will receive 70 CGE in 35 fractions at 2 CGE per fraction. An additional of boost of 6 CGE in 3 fractions to the primary gross tumor volume for patients with large primary tumors is at the discretion of the physician.

6.4.1.2 The lymph node metastasis of 1 - 2 cm, PTV₆₆, will receive 66 CGE in 33 fractions at 2 CGE per fraction.

6.4.1.3 The primary subclinical and the high risk nodal region (PTV₆₀) will receive 30 fractions of 2.0 CGE per fraction, total 60 CGE.

6.4.1.4 The low neck (including) supraclavicular field will be treated with conventional AP field or AP/PA fields at the discretion of the physician, and will receive 25 - 27 fractions of 2.0 CGE/fraction to a total 50 - 54 CGE unless there are gross nodes in which all the gross nodes should receive the same dose as the PTV₆₆₋₇₀.

6.4.1.5 PTV₇₀ and PTV₆₀ of the upper field will be treated with a combination of proton beam and photon radiation. The low neck will be treated with photon only.

6.4.1.6 The prescription dose is the isodose surface that encompasses at least 95% of the planning target volume (PTV). No more than 20% of any PTV₇₀ will receive $\geq 110\%$ of the prescribed dose. No more than 1% of any PTV₇₀ and any PTV₆₀ will receive $\leq 93\%$ of the prescribed dose. No more than 1% or 1 cc of the tissue outside the PTVs will receive $\geq 110\%$ of the dose prescribed to the PTV₇₀.

Table 1. Radiation dose summary

Target	Dose	Designation
Primary Gross Disease	70 CGE	PTV ₇₀
Nodal Disease > 2cm	70 CGE	PTV ₇₀
Nodal Disease 1 - 2cm	66 CGE	PTV ₆₆
Primary subclinical	60 CGE	PTV ₆₀
High risk nodal region	60 CGE	PTV ₆₀
Low neck	50-54 CGE	PTV ₅₀₋₅₄

6.4.2 DVH's must be generated for all critical normal structures and the unspecified tissues.

Table 2. Dose constraints to critical tissues

Normal tissues	Total dose (CGE)	Dose per fraction (CGE)
Brainstem (surface)	$\leq 60 - 64$	≤ 2.0
Brainstem (center)	< 54	≤ 2.0
Spinal Cord (surface)	≤ 50	≤ 2.0
Spinal Cord (center)	≤ 45	≤ 2.0
Optic nerves	$\leq 54 - 63$	≤ 2.0
Chiasm	$\leq 54 - 63$	≤ 2.0
Retina	≤ 45	≤ 2.0
Temporal/frontal lobes	≤ 70	≤ 2.0

6.4.3 Other Normal Structures

Parotid glands: Mean dose ≤ 26 CGE (*at least one gland*), or at least 20 cc of the combined volume of both parotid glands will receive < 20 CGE or at least 50% of the gland will receive < 30 CGE (*should be achieved in at least one gland*).

Table 3. Dose constraints to normal tissues

Normal tissues	Total dose (CGE)
Lacrimal gland	≤ 44
Submandibular glands	reduce the dose as much as possible
Cochleas	reduce the dose as much as possible
Temporomandibular joints	reduce the dose as much as possible
Mandible	reduce the dose as much as possible
Lens	reduce the dose as much as possible
Oral cavity	reduce the dose as much as possible
Pituitary	reduce the dose as much as possible
Hypothalamus	reduce the dose as much as possible
Larynx	≤ 45 CGE
Esophagus	reduce the dose as much as possible
Swallowing Structures	reduce the dose as much as possible
Mastication Muscles	reduce the dose as much as possible

6.4.4 Planning Priorities

Critical normal structure constraints followed by the prescription goals are the most important planning priorities. The priorities in addressing the protocol aims and constraints will be in the following order:

- 1) Critical and normal structure constraints

-
- 2) Dose specifications
 - 3) Planning Goals: other normal structures

6.5 Chemotherapy

6.5.1 Cisplatin

6.5.1.1 Mechanism of Action: The dominant mode of action of cisplatin appears to be inhibition of the incorporation of DNA precursors, although protein and RNA synthesis are also inhibited. Plasma levels of cisplatin decay in a biphasic mode with an initial half-life of 25 to 49 minutes, and a secondary phase ranging from 58 to 73 hours. This prolonged phase is due to protein binding which exceeds 90% of the radioactivity in the second phase. Urinary excretion is incomplete with only 27 to 45% of the radioactivity excreted in the first five days. The initial fractions of radioactivity are largely unchanged drugs. Although this drug seems to act as an alkylating agent, there are data to indicate that its mode and sites of action are different from those of nitrogen mustard and the standard alkylating agents.

6.5.1.2 Formulation: Cisplatin is available as a liquid (concentration 1 mg/ml) in a 100 ml vial.

6.5.1.3 Preparation: Aluminum reacts with cisplatin causing precipitation formation and loss of potency; therefore, needles or intravenous sets containing aluminum parts that may come in contact with the drug must not be used for the preparation or administration of cisplatin.

6.5.1.4 Storage: Cisplatin should be kept at room temperature to avoid precipitation. The solution may be further diluted in a chloride-containing vehicle such as D5NS, NS, or D51/2NS (precipitate occurs in D5W). Cisplatin has been shown to react with aluminum needles, producing a black precipitate within 30 minutes.

6.5.1.5 Administration: Cisplatin should be given immediately after preparation as a slow intravenous infusion.

6.5.1.6 Adverse Effects: Incidence rates of adverse events associated with cisplatin are provided in the product package insert. The following events are expected with the administration of cisplatin:

-

- 6.5.1.7 Nephrotoxicity: Dose-related and cumulative renal insufficiency is the major dose-limiting toxicity of cisplatin. Renal toxicity has been noted in 28 - 36% of patients treated with a single dose of 50 mg/m². It is first noted in the second week after a dose and is manifested as elevated BUN, creatinine, and serum uric acid, or as a decrease in creatinine clearance. Because renal toxicity becomes more prolonged and severe with repeated courses of cisplatin, renal function must return to normal before another dose can be given.
- 6.5.1.8 Ototoxicity: Ototoxicity has been observed in up to 31% of patients treated with a single dose of cisplatin 50 mg/m². It is manifested by tinnitus and/or hearing loss in the high frequency range. Deafness has been reported rarely.
- 6.5.1.9 Hematologic Toxicity: Myelosuppression occurs in 25 - 30% of patients treated with cisplatin. Nadirs in circulating platelets and leukocytes occur between Days 18 and 23 with most patients recovering by Day 39 or sooner. Thrombocytopenia, anemia, neutropenia, and fever are also possible adverse events. The occurrence of acute leukemia has been reported rarely in patients treated with anthracycline/alkylator combination chemotherapy.
- 6.5.1.10 Gastrointestinal Toxicity: Marked nausea and vomiting occur in almost all patients treated with cisplatin. Diarrhea and anorexia have also been reported.
- 6.5.1.11 Neurotoxicity: Neurotoxicity, usually characterized by peripheral neuropathies, has been reported. Neuropathy usually occurs after prolonged therapy (4 to 7 months); however, symptoms have been reported after a single dose. Muscle cramps, loss of taste, seizures, autonomic neuropathy, dorsal column myelopathy, and Lhermitte's sign have also been reported.
- 6.5.1.12 Ocular Toxicity: Optic neuritis, papilledema, and cerebral blindness have been reported infrequently in patients receiving standard recommended doses of cisplatin. Blurred vision and altered color perception have been reported after the use of regimens with higher doses of cisplatin or greater dose frequency than those recommended in the package insert.
- 6.5.1.13 Anaphylactic-like Reactions: Anaphylactic-like reactions have occasionally been reported in patients previously exposed to

-
cisplatin. Symptoms include facial edema, wheezing, tachycardia, and hypotension.

6.5.1.14 Hepatotoxicity: Transient elevations in liver enzymes, especially SGOT (*AST*), and bilirubin, have been reported.

6.5.1.15 Other Toxicities: Other infrequent toxicities that have been reported include cardiac abnormalities, hiccups, elevated serum amylase, rash, alopecia, malaise, and asthenia. Rare cases of local soft tissue toxicity have occurred.

6.5.1.16 Supplier: Commercially available.

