6.5.6 Cisplatin Dose Adjustments

6.5.6.1 Neutropenia

Treatment can be delayed for up to 2 weeks until ANC is $\geq 1500/\text{mm}^3$. However, if the counts have not recovered in 2 weeks, the patient should go off chemotherapy. Dose reductions for reduced ANC are not based on a single nadir count. The ANC must remain $< 500/\text{mm}^3$ for > 5 days before a dose reduction is made. If the results of the scheduled weekly complete blood count documents an ANC of $< 500/\text{mm}^3$, repeat counts are to be obtained every other day until the ANC recovers to a level of $> 500/\text{mm}^3$. If chemotherapy must be withheld due to neutropenia, complete blood count should be obtained weekly until the counts reach the lower limits for treatment as outlined.

Table 6. Cisplatin dose modifications in neutopenia

Nadir of last cycle		% Dose of cisplatin from starting dose
	ANC* on day 1 of each cycle < 1500	ANC* on day 1 of each cycle ≥ 1500
Febrile neutropenia (regardless of duration)	Hold	100%
< 500 for < 5 days	Hold	100%
< 500 for ≥ 5 days	Hold	80%

* ANC = absolute neutrophil count

ANC must be $\geq 1,500/\text{mm}^3$ on day 1 of each cycle. Reduce doses only for ANC is $< 500/\text{mm}^3$ for ≥ 5 days.

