9.0 Data Collection

Table 13. Evaluations before, during, and after chemoradiation

	Pre-study (timing before study entry)	Pre-treatment	During chemoradiation^b	During chemotherapy alone	Follow-up^c
History & physical	14 days		X	X	X
Disease	8 weeks				X

Version 2.0

Date: 6.21.2011

-

documentation	(*EUA)				
Dental evaluation		6 months			
Tobacco and alcohol assessment		14 days			
Nutritional evaluation		1 month			
Patient swallowing diary		14 days	X		1.5, 3, 12, 24 months ⁱ
CBC/platelets	14 days		X	X ^h	X
Chemistry (alkaline phosphatase ^a , AST, ALT, bilirubin, BUN, serum creatinine, creatinine clearance (if indicated), electrolytes (Na, K, Mg, Cl), calcium, protein, albumin, urinalysis (if indicated))	14 days		X (Weekly for BUN and creatinine. Every 3 weeks for the others)	X (Every 3 weeks)	
β-HCG for females at risk for pregnancy	14 days				
Thyroid function panel (TSH, T3, T4)	14 days				X ^l
Chest X-ray or CT	1 month				X ^d
CT/MRI of H&N	1 month				X ^d
PET/CT ^f		1 month			X
Toxicity evaluation			X	X ^c	X
Swallow study		21 days			3, 12, 24 months ⁱ
Salivary study		21 days			3, 6, 12, 24 months ⁱ
Speech assessment (HNHSAI)		14 days			1.5, 3, 6, 12, 24 months ⁱ
Subjective QOL		14 days			1.5, 3, 6, 12, 24 months ⁱ
Physician dysphagia log		14 days			1.5, 3, 6, 12, 24 months ⁱ

Audiogram	6 weeks				X ^g
Chemosensory questionnaire (CSQ)		14 days			1.5,3,6,12,24 months ⁱ
Trismus assessment		14 days			1.5,3,6,12,24 months ⁱ

* EUA = examination under anesthesia

X denotes the type of evaluation that needs to be performed during the study period.

- a. Liver CT or MRI must be done in presence of elevated alkaline phosphatase, AST, or bilirubin or other clinical indicator; bone scan must be done in presence of elevated alkaline phosphatase or other clinical indicator.
- b. Weekly during radiotherapy.
- c. Follow-up will be performed after radiation and then every 3 (+/- 3 weeks) months during the first two years; every 6 (+/- 3 months) months during years 3 - 5; then annually (+/- 6 months). After year 5, patients are encouraged to continue with the follow-up appointments and studies annually (+/- 6 months). All follow-up appointments and studies may be performed at non-participating institutions with results sent to the participating institutions for review.
- d. These tests will be performed at least every 6 months (+/- 3 months) during the first 3 years; the first CT/MRI of nasopharynx will be performed at approximately 2 months after radiation.

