- e. Prior to each cycle.
- f. PET/CT is optional but encouraged. It will be performed prior to treatment (must be ≤ 21 days prior to study entry), at approximately 2 months after radiation, and every 6 months during the first 3 years.
- g. Yearly (+/- 6 months) or clinically indicated. Once patients have reached the 24-month follow-up time point, patients are encouraged but not required to perform these studies at their annual (+/- 6 months) follow-up appointments.
- h. Every three weeks, or more frequently as clinically indicated. CBC/platelets must be drawn before treatment, either on day 1 of each cycle or no more than 72 hours in advance of each cycle.
- i. The 1.5 month studies will be performed at 1.5 (+/- 1) month after radiation, 3-month studies will be performed at 3 months (+/- 6 weeks), the 6-month studies will be performed at 6 (+/- 3) months, the 12-month studies will be performed at 6 (+/- 3 months), and the 24-month studies will be performed at 24 (+/- 6) months. Once patients have reached the 24-month follow-up time point, Patients are encouraged but not required to perform these studies at their annual (+/- 6 months) follow-up appointments.

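### The nadir that sets the first adjuvant cisplatin dose falls between Table 13's dated blood counts, and section 6.5.6.1 presumes a weekly count that Table 13 does not schedule there

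*Combined protocol and SAP*

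**What the plan says.** **Nadir timing.** Section 6.5.1.9, on cisplatin: "Nadirs in circulating platelets and leukocytes occur between Days 18 and 23 with most patients recovering by Day 39 or sooner".

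**Dose rules.** Tables 6 and 7 (sections 6.5.6.1 and 6.5.6.2) set the cisplatin dose from the nadir of the last cycle, once the day-1 count is adequate (ANC at least 1500, platelets at least 100,000). The percentages are labelled "Dose of cisplatin from starting dose".
- Table 6 gives 80% after an ANC below 500 for at least 5 days.
- Table 7 gives 80% after a first platelet nadir below 50,000 and 60% after a second.
- Neither table makes an exception for adjuvant cycle 1.

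**Neutrophil follow-up.** Section 6.5.6.1 says "Dose reductions for reduced ANC are not based on a single nadir count". It continues "If the results of the scheduled weekly complete blood count documents an ANC of" below 500, then repeat counts are taken every other day until recovery.

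**CBC schedule in Table 13.**
- During chemoradiation (footnote b): "Weekly during radiotherapy".
- During chemotherapy alone (footnote h): "Every three weeks, or more frequently as clinically indicated", and also "CBC/platelets must be drawn before treatment, either on day 1 of each cycle or no more than 72 hours in advance of each cycle".
- Follow-up (footnote c), a column that includes a CBC: "Follow-up will be performed after radiation and then every 3 (+/- 3 weeks) months during the first two years".

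**The concern.** The dose rule needs a measurement that the visit schedule does not secure. For adjuvant cycle 1 the last cycle is the day-43 concurrent dose. Its nadir comes after the weekly counts have stopped and, in most allowed calendars, before the pre-adjuvant draw. The one other CBC in Table 13 that could fall in between, at the visit after radiation, is undated.

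At stake is the reduction for a deep nadir that has since recovered. A platelet nadir below 50,000, or an ANC below 500 for 5 days or more, would call for 80% of the dose at adjuvant cycle 1. If nobody measured it, the patient gets the full dose, and a later platelet fall that should count as the second occurrence is treated as the first. Chemotherapy may be given at any participating institution (section 6.0), so sites may resolve the unclear schedule differently.

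**Working it through.** **Inputs**
- Schema: concurrent cisplatin on days 1, 22 and 43; first dose within the first three days of radiation; treatment Monday to Friday, starting on a Monday to Thursday; radiotherapy shown over days 1 to 54.
- 6.4.1.1: 35 fractions, or 38 with the optional boost.
- 6.5.1.9: nadir on days 18 to 23, most patients recovered by day 39.
- 6.5.3: adjuvant start 3 to 8 weeks after radiation; chemotherapy up to 2 days early or late.
- Table 13, footnote h: pre-cycle draw on day 1 or up to 72 hours before.
- 6.5.4.2: adjuvant cisplatin 80 mg/m².

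**Step 1. Last day of radiotherapy, without breaks**

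| Start | 35 fractions | 38 fractions |
|---|---|---|
| Monday | 47 | 52 |
| Tuesday | 49 | 52 |
| Wednesday | 49 | 52 |
| Thursday | 49 | 54 |

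The longest case reproduces the schema's day 54.

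**Step 2. Nadir window after the day-43 dose**
- Dose day counted as day 1: 43 + 17 = 60 to 43 + 22 = 65.
- Dose day counted as day 0: 43 + 18 = 61 to 43 + 23 = 66.
- Both conventions together: days 60 to 66.

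**Step 3. Weekly CBCs.** They end on day 54 at the latest, 60 − 54 = 6 days before the window opens. The three-day start rule and the 2-day allowance let dose 3 move to days 41 to 47. Even at day 41 the window opens on 41 + 17 = 58, still after day 54.

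**Step 4. Pre-adjuvant draw.** The adjuvant start is the last radiotherapy day plus 21 to 56, and the draw is on that day or up to 3 days earlier. For a draw by day 66, the start must be no later than 66 + 3 = 69.
- Last radiotherapy day 47: start on day 68 or 69 qualifies. With last day 49, 52 or 54, the earliest start is 70, 73 or 75, so none does. That is 2 of 8 × 36 = 288 allowed calendars.
- If the start may also be 2 days early (plus 19 to 56): 4 calendars for last day 47 (starts 66 to 69) and 2 for each of the three schedules ending on day 49 (starts 68 and 69). That is 4 + 6 = 10 of 8 × 38 = 304, or 3.3%.
- With dose 3 anywhere on days 41 to 47, the range is 0 of 288 to 36 of 304 (11.8%).

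**Step 5. Can the count have recovered by adjuvant day 1?** Day 39 after the dose is study day 43 + 38 = 81 or 43 + 39 = 82. The adjuvant start lies between 47 + 21 = 68 and 54 + 56 = 110. A patient can therefore pass the day-1 thresholds, on an allowed calendar, after an unmeasured deep nadir.

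**Step 6. Dose consequence at 80 mg/m²**
- Reduction missed at adjuvant cycle 1: 80 given instead of 0.8 × 80 = 64; 80/64 = 1.25.
- Later second platelet occurrence counted as the first: 64 given instead of 0.6 × 80 = 48; 64/48 = 1.33.

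**The case against.** The strongest reply is that the protocol already has the count. Section 6.5.6.1 speaks of a scheduled weekly CBC without limiting it to radiotherapy, and it governs the very table in question. Footnote h adds a three-week interval: counted from the day-43 pre-dose draw (day 40 to 43), it lands on day 61 to 64, inside the window. Footnote c requires a visit with a CBC after radiation. A site that reads these generously would catch the nadir.

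Much of this stands. It makes the point a disagreement between sections, not a missing safeguard. It does not remove the point: Table 13 schedules weekly counts only during radiotherapy, footnote h is attached to the chemotherapy-alone column, and footnote c's visit has no date. Nothing says which provision governs the weeks before adjuvant cycle 1.

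Three further replies also stand in part.
- The day-1 thresholds block treatment on low counts. They do not replace Tables 6 and 7, which reduce the dose after recovery.
- A draw after day 66 may still find a count below 50,000 in a slow recoverer. The patient who recovers quickly is the one missed.
- Breaks in radiotherapy extend the weekly counts. Five missed fractions would move the longest schedule's last day from 54 to 54 + 7 = 61. A gap that closes only when treatment is interrupted is still a gap in the plan.

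**Conclusion.** The point holds as a minor inconsistency. Followed as written, Table 13 does not ensure that the nadir of the day-43 dose is measured, although Tables 6 and 7 need it for adjuvant cycle 1. The possible overdose relative to the protocol's own rule is 25% at that cycle (80 versus 64 mg/m²), and 33% at a later cycle if a second platelet occurrence is taken for the first (64 versus 48 mg/m²).

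This rests on radiotherapy without breaks, a third concurrent dose given as cisplatin, the nadir window of 6.5.1.9, and a starting dose of 80 mg/m² in the adjuvant phase. The number of patients affected cannot be estimated from the documents.

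A reader might infer more than the documents support:
- *That patients could be dosed on unrecovered counts.* The day-1 thresholds prevent this.
- *That the calendar shares in step 4 are risks.* They weight every allowed calendar equally and leave out the undated visit and any weekly count under 6.5.6.1.
- *That the gap extends to the carboplatin rules, or that the nadirs of the other cycles are secured.* The window is stated for cisplatin only. No nadir timing is given for carboplatin or for cisplatin with 5-FU, so neither can be judged.
- *That the starting dose might mean 100 mg/m² in the adjuvant phase.* The 100% entries of Tables 6 and 7 would then order 100 mg/m², against the 80 mg/m² of 6.5.4.2.
- *That the primary analysis is affected.* Section 11.0 counts chemotherapy courses received, not dose, so a skipped reduction does not itself change the 18-of-25 rule in section 12.0. No sample size or error rate changes.

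**What to change.** For patients given the third concurrent cisplatin dose, do one of the following:
- In footnote c of Table 13, date the CBC and platelets of the existing post-radiation visit to days 18 to 23 after that dose. This draw always falls inside the window.
- Or state in Table 13 that the weekly CBC of 6.5.6.1 continues until adjuvant day 1. A weekly draw falls in the six-day window or within one day of it.

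Under either option, apply the existing every-other-day repeats if the ANC is below 500, because one count cannot show how long it stayed there. State that the result is the nadir of the last cycle for adjuvant cycle 1 in Tables 6 and 7.

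The cost is small: the timing of one visit becomes fixed, or a few more blood counts are taken, with occasional repeats. Some first adjuvant doses may be reduced that would otherwise have been given in full.
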